Appendix 1: Validation of "non-vaccine serotypes" as control group using other control groups

The use of the indirect cohort method implies that the serotyping results are available for all or a systematic sample of IPD or SpCAP cases. This assumption should be validated by comparing the VE results with those of other controls groups using the same data sources.

Below we present advantages and disadvantages of each additional groups and specific features for analyses.

Using a unique identifier allows linkage of various datasets:

- hospital discharge register diagnosis codes;
- laboratory data;
- vaccination data.

This constitutes the unique opportunity to measure effectiveness using different control groups and evaluate which one better represents the vaccination coverage of the population that gives rise to IPD/SpCAP caused by vaccine serotypes.

These additional control groups could be:

- 1. Hospitalised elderly according to other disease codes:
 - a. hospitalised elderly≥65 years for other ICD codes than pneumococcal related codes as presented in Table 4.
 - b. hospitalised elderly ≥65 years for condition that do not include those considered high risk for IPD/SpCAP (i.e. ICD9CM 800-999 or ICD10CM: S00-T98: Injury and poisoning).

Advantages:

- Feasibility (access to the data)
- Same type of data available
- Can compute VE against all type IPD/SpCAP

Disadvantages:

- Susceptible to selection bias: the control group might not represent in terms of exposure the population given rise to the pneumococcal cases
- Need for adjustment for different confounders: severity of disease, access to care (information not always available)
- 2. Controls from community
 - a. Screening method using the vaccination coverage of the elderly by age and risk groups

Advantages:

- Quick analysis when incidence rates are not available
- Could be done only with data readily available for surveillance or available surveys
- Can be used for other outcomes such as all type IPD/SpCAP
- Adjustment difficult but possible for some factors (age groups, high risk groups) if vaccination coverage is available by group

Disadvantages:

- VC in the population might not represent the one of the source population of pneumococcal hospitalised cases
- VE estimates are highly dependent on time period during which it is used and the choice of outcome (VT versus all type IPD/SpCAP)

Vaccine coverage in the reference group

Vaccine coverage can be measured using different population sub-groups (from now on called reference groups). The best reference group will be the one representing the vaccination coverage in the population giving rise to the cases.

The size of the reference group should be large (> 1000 individuals).

Examples of sources for vaccination coverage include:

- For GPs with computerised medical records, vaccination coverage can be extracted from the GP's database;
- For GPs without computerised medical records, a sample of patients in a defined time period may be selected and influenza vaccination status documented;
- For GPs without computerised medical records, a sample of the population in the catchment area can be selected and interviewed on their influenza vaccination status (telephone, face to face):
 - Vaccination registries;
 - Health insurance claims data;
 - National surveys;
 - Vaccines distributed, vaccines sales in pharmacies.

Analysis

Measure of effect

When looking within populations where the coverage represents the same population as the cases, the VE against each of the outcomes selected (e.g IPD, SpCAP or pneumococcus serotype outcome) can be calculated as 1- odds of vaccination in cases / odds of vaccination in the population, or:

in which PPV is the proportion of the reference group vaccinated (vaccine coverage in the reference group), and PCV the proportion of influenza cases vaccinated.

Ninety five percent confidence intervals will be computed using the Farrington method²⁴.

TECHNICAL DOCUMENT – Protocol on effectiveness of Pneumo vaccines in elderly

²⁴ Farrington CP. Estimation of vaccine effectiveness using the screening method. Int J Epidemiol. 1993 Aug;22(4):742–6.

Stratified analysis

Analysis will be stratified according to the availability of vaccination coverage in the reference group:

- age groups (<75 and >74 years);
- underlying conditions

These analyses could only be performed if appropriate sample size in each stratum could be reached.

Adjusted analysis, Farrington method

Each case is matched to the coverage from the population that best matches that case according to key confounding variables such as age, chronic conditions and time period. The analysis is then performed as a logistic regression with an offset as the logit of the matched coverage²⁵.

These variables are included in the model to look at the interaction and define if there is effect modification. If effect modification is identified, then a stratified analysis will be conducted. The analysis can be done only if PCV and PPV are available by the effect modifiers strata:

Logit [PCV] = logit[PPV] + a +
$$b_xX_x$$
 +... b_kX_k

An adjusted VE and its 95% CI will be obtained.

► Each study site to describe additional studies used to validate the indirect cohort method.

-

²⁵ Idem 24

Version number	Date published	Text in original document	Changes included in the amended version	Comments
V2.1	15 Dec 2016	Page 14 (secondary outcomes) Page 14 (Case definitions for secondary outcomes) Table 3 "Clinical presentation (meningitis, pneumonia, sepsis)"	Modified by "Clinical presentation (meningitis, bacteraemic pneumonia, bacteraemia, other clinical presentations)"	Note that bacteraemia covers all bacteremia and not only bacteremia without focus (because in Denmark no difference between pneumonia and bacteremic pneumonia can be made) Decision during the technical meeting (Paris, September 2016) because the definition of sepsis is not homogenous over the sites.
		Page 15 (Case definitions for secondary outcomes and reference group) "Severity is assessed according to: ICU admission and/or length of hospital stay >14 days and/or presence of septic shock and/or intra-hospital death"	Modified as: "Severity is assessed according to: ICU admission and/or length of hospital stay >14 days and/or death within 30 days"	Decision during the technical meeting (Paris, September 2016
		Page 17: Definition of vaccination status	Included a definition for repeated vaccination	Decision during the technical meeting (Paris, September 2016)
		Page 17-18: confounders and effect modifiers Table 4: text replaced by the ICD codes for risk conditions	Modified to include the ICD codes for the underlying conditions	Decision during the technical meeting (Paris, September 2016)

		Table 4 ICD codes for IPD and SpCAP	Table 4 becomes table 2 and includes ICD codes for clinical IPD and SpCAP	Decision during the technical meeting (Paris, September 2016)
		Table 4: ICD codes for the underlying conditions by immune status	The new table 4 includes ICD 9 and 10 codes for underlying conditions	Decision during the technical meeting (Paris, September 2016)
v2.2	15 Dec 2017	Table 3 List of variables, coding, definitions and data sources, as collected in the IPD surveillance systems (harmonised under the SpIDnet/I-MOVE+ project)		•

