4.5.4 Cases and controls inclusion and exclusion criteria

IPD/SpCAP cases and controls will be included if individuals are eligible for PCV13 or PPSV23 vaccination, were hospitalised for an IPD or SpCAP, and have had the serotype identified.

IPD cases and controls will be excluded if:

-

²³ Andrews, N., et al. Impact and effectiveness of 23-valent pneumococcal polysaccharide vaccine against invasive pneumococcal disease in the elderly in England and Wales. Vaccine 2012: 30, 6802–6808

- Individuals are not eligible for vaccination due to conditions that contra-indicate vaccination;
- Testing of non-sterile body fluid was used for diagnosis;
- Recurrent invasive disease is diagnosed (only the first episode will be included in the analysis). Recurrent invasive disease is defined as IPD episodes in the same individual with the diagnosis/admission date at 30 days apart or identification of the same serotype.
- Serotyping could not be performed.

SpCAP cases and controls will be excluded if:

- Individuals are not eligible for vaccination due to conditions that contra-indicate vaccination;
- Recurrent disease is diagnosed (only the first episode will be included in the analysis). Recurrent
 disease is defined as SpCAP episodes in the same individual with the diagnosis/admission date at 30
 days apart or identification of the same serotype.
- Serotyping could not be performed.

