4.5.5 Laboratory methods

To comply with the IPD case definition, laboratory confirmation through culture, PCR or antigen detection could be used for diagnosis in order to allow serotyping. Serotyping is of paramount importance as it is required for IPD cases inclusion and it makes the differentiation between cases and controls.

- Isolation and identification/ PCR could be done at the hospital laboratory or at the reference laboratory
- Serotyping of isolates is usually done at the reference laboratory using capsular reaction testing (Quellung test), PCR or gel diffusion with type-specific antisera
- Antimicrobial susceptibility testing should be done for all isolates for at least the following antimicrobials: penicillin, macrolide, and cephalosporin. MIC will be reported and EUCAST clinical breakpoints used will be used for classification

Specimen collection, transportation and tests used are well defined in case an IPD surveillance system is in place.

For non-invasive SpCAP, the diagnosis can be made using similar tests from non-sterile fluids (sputum, tracheobronchial aspirates, urine, etc.) or the urine antigen testing which allows serotyping.

▶ Each study site to describe how specimens are collected, transported and types of the tests performed for confirmation and serotyping. When confirmation and serotyping was done by PCR, the method and the algorithms used should be described. The sensitivity and specificity of all tests should be provided.

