5.1 Data checking

As much as possible, data should be completed or validated against the data source. Data will be checked to find outliers, implausible or missing information. The inclusion and exclusion criteria will be checked for the studies using IPD surveillance. If the following variables are missing, cases will be excluded:

- Date of birth/ age;
- Date of onset /hospital admission /diagnosis;
- Serotype.

Baseline characteristics of records with missing serotype will be compared to records without missing serotype in order to assess the bias due to differential serotyping by vaccination status.

For all the other variables, baseline characteristics of records with missing data will be compared to records without missing data. If there is no evidence of bias in the missing data, the distribution of IPD/SpCAP cases with known data will be applied to the cases with missing results. If a high proportion of data are missing and/or there is no evidence of bias in the missing data, and variables that are considered good predictors of the missing data are available, multiple imputation using chained equations can be used to replace missing values.

- Each study site to describe the data cleaning process and the management of missing data
- ► Each study site to specify the percentage of missing by variable collected and assess differences between serotyped and non-serotyped IPD/SpCAP cases.

TECHNICAL DOCUMENT – Protocol on effectiveness of Pneumo vaccines in elderly

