5.3 Measure of association

Vaccine effectiveness will be computed as 100% X (1 – the odds of vaccination in VT cases / odds of vaccination in NVT controls). An exact 95% confidence interval will be computed around the point estimate. The crude and adjusted estimates of vaccine effectiveness will be provided.

The VE will be computed for all exposures mentioned above.

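### Appendix 1 proposes to validate complete or systematic serotyping by comparing VE across control groups, but that comparison cannot test it: both disagreement and agreement can mislead.

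*Protocol*

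**What the plan says.** Appendix 1 opens by saying that the indirect cohort method "implies that the serotyping results are available for all or a systematic sample of IPD or SpCAP cases". The next sentence is "This assumption should be validated by comparing the VE results with those of other controls groups using the same data sources". Completeness of serotyping is the only thing that the words at the start of that sentence can refer to. The comparators then listed are elderly patients hospitalised for other conditions and, through the screening method, vaccination coverage in the population.

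The title of the Appendix and a later sentence give a different aim: to find which control group best reflects coverage in the population that produces the VT cases.

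Four other places bear on the point:
- Section 4.5.4 admits cases and controls alike only if they "were hospitalised for an IPD or SpCAP, and have had the serotype identified". Section 4.5.5 says of serotyping that "it makes the differentiation between cases and controls".
- Section 5.3 defines indirect-cohort VE as one minus "the odds of vaccination in VT cases / odds of vaccination in NVT controls".
- Appendix 1 defines the screening VE as "1- odds of vaccination in cases / odds of vaccination in the population".
- Section 5.1 compares records with and without a serotype "in order to assess the bias due to differential serotyping by vaccination status".

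**The concern.** Two assumptions are merged and given one check. The first is that serotyping is complete or systematic. The second is that NVT controls carry the vaccination odds of the source population. Comparing VE across control groups speaks to the second. It is offered as the test of the first.

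The indirect cohort selects both of its groups on serotyping, whereas the comparators select only the VT cases. Uneven serotyping by vaccination status can therefore leave the indirect cohort right and the comparator wrong, and a site following the Appendix would read the gap as a fault in the indirect cohort. A form of uneven serotyping that does bias the indirect cohort can bias the comparator equally, and the check would then reassure. Because this is a generic protocol that asks every site to describe how it validates the method, the confusion would pass to each site and to the pooled estimate.

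**Working it through.** **Inputs.** The estimators come from Section 5.3 and Appendix 1, and selection on serotyping from Section 4.5.4. True VE of 60% and coverage of 0.5 lie on the Table 4 grid. The serotyping fractions are assumptions, since the protocol gives none; values from 60% to 80% are used in step 2 and from 55% to 95% in step 4.

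**Step 1. The protocol's own bias figure.** The protocol has no figure for serotyping bias. Its worked bias formula, in Section 6.1, is for serotype replacement: VE_Broome = 1 − (1 − VE)/(1 + VEc·Pu/(1 − Pu)).
- VE 90%, VEc 50%, Pu 40%: 1 − 0.10/1.333 = 92.5%, as stated.
- VE 70%, VEc 30%, Pu 40%: 1 − 0.30/1.20 = 75%, as stated.

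The denominator is the factor by which replacement raises the vaccination odds of NVT controls. It is used in step 3.

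**Step 2. Serotyping depends on vaccination status only.** Let a and b be vaccinated and unvaccinated VT patients, c and d the same for NVT, and sv and su the serotyping probabilities in vaccinated and unvaccinated patients.
- Indirect cohort: OR = (a·sv / b·su) / (c·sv / d·su) = ad/bc, which is unchanged.
- Comparator: OR = (a·sv / b·su) / source odds = true OR × sv/su.

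With true OR 0.40:

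| sv/su in % | Ratio | Indirect VE | Comparator VE | Vaccinated share of serotyped NVT (source 0.50) |
|---|---|---|---|---|
| 80/70 | 1.143 | 60% | 1 − 0.457 = 54.3% | 0.533 |
| 80/60 | 1.333 | 60% | 1 − 0.533 = 46.7% | 0.571 |
| 60/80 | 0.750 | 60% | 1 − 0.300 = 70.0% | 0.429 |

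The same cancellation holds if serotyping also depends on serotype, provided the two effects multiply.

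**Step 3. One disagreement, two causes.** Take true VE 60% and the Section 6.1 values Pu 40% and VEc 50%, which give a factor of 1.333.
- Replacement with complete serotyping: the indirect cohort gives 1 − 0.40/1.333 = 70% and the comparator 60%. The ratio of the (1 − VE) terms, comparator over indirect, is 0.40/0.30 = 1.33. The indirect cohort is wrong.
- No replacement, serotyping 80/60: the indirect cohort gives 60% and the comparator 46.7%. The ratio is 0.533/0.40 = 1.33. The comparator is wrong.

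The relative gap is identical, so the comparison alone cannot say which estimate to distrust. Weighting serotyped patients by 1/sv and 1/su separates the two: the NVT-to-source odds ratio returns to 1.00 in the second case and stays at 1.33 in the first.

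**Step 4. Serotyping depends jointly on vaccination and serotype.** The indirect OR is then the true OR × (s_vVT/s_uVT)/(s_vNVT/s_uNVT), and the comparator OR is the true OR × s_vVT/s_uVT. True VE is again 60%.
- Vaccinated VT 0.6, all others 0.9: both ORs are 0.40 × 0.667 = 0.267, so both VEs are 73.3%. The check passes a biased estimate.
- Vaccinated NVT 0.6, all others 0.9: indirect OR 0.40/0.667 = 0.60, VE 40%; comparator VE 60%.
- Vaccinated VT 0.95, vaccinated NVT 0.75, unvaccinated VT 0.75, unvaccinated NVT 0.55: indirect VE 62.8%, comparator VE 49.3%. Both are biased, by different amounts.

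**The case against.** The strongest reply is that this is one badly placed sentence. The title of the Appendix and its later text already state the representativeness aim, and Sections 1.2 and 6.2.5 treat representativeness as the core assumption. The Appendix does not hold up the comparators as a gold standard: it says hospital controls are open to selection bias and population coverage may not match the source population. Section 5.1 checks serotyped against unserotyped records directly. All of this stands, and it limits the consequence. It does not make the stated check valid for the stated assumption, and nothing in the protocol tells a site that uneven serotyping by vaccination status falls on the comparators.

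Three stronger readings are tempting and are not supported.

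- A reader might infer that the Appendix would reject a valid indirect cohort at some known, high rate. In simulations at the Table 4 size of 255 cases and 170 controls (coverage 0.5, VE 60%), the share of studies flagged at 80/70, 80/60 and 60/80 is 15%, 48% and 48% if NVT odds are tested directly against known coverage. It is about 12%, 40% and 40% with a reference group of 1000, about 1%, 11% and 7% if the two VEs are treated as independent, and under 1% by interval overlap. The protocol prescribes none of these rules, so no single rate can be charged to it.
- A reader might infer that differential serotyping never harms the indirect cohort. Step 4 shows otherwise. The protocol itself suggests a route: the Introduction says serotypes differ in clinical presentation, and Section 6.2.6 says testing follows presentation and severity.
- A reader might infer that the Section 5.1 comparison is mistaken and should go. It is needed, because differential serotyping by vaccination status does bias the Appendix 1 comparators, and the comparison supplies the fractions for weighting.

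Comparators for all-type disease need no serotype and escape the problem. Section 1.2, however, says the indirect cohort cannot estimate all-type VE, so there is nothing to set them against.

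**Conclusion.** The point holds. The check that Appendix 1 prescribes cannot test the assumption that it names. Under serotyping that depends on vaccination status and not jointly on serotype, the indirect cohort is unaffected and the VT comparator is off by the factor sv/su: 6 points low, 13 points low or 10 points high at true VE 60% for the three patterns tried. Under joint dependence the indirect cohort is biased as well, and agreement can hide it, as when both methods give 73% for a true 60%.

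These sizes rest on assumed serotyping fractions; the protocol does not suggest how large such gaps are in practice. With no decision rule in the Appendix, the harm is that a disagreement or an agreement is misread. Using other control groups to examine whether NVT controls are representative remains sound and should stay.

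**What to change.** 1. In Appendix 1, state that comparing control groups tests whether NVT controls have the vaccination odds of the source population, and does not test whether serotyping is complete.
2. For the hospital-control and screening VE against VT disease, and for the comparison itself, weight serotyped patients by the inverse of the serotyping fraction by vaccination status, and by age group and year where numbers allow. Report the ratio of NVT to comparator vaccination odds with its 95% CI. Sites must keep the vaccination status of unserotyped patients for this; the Section 5.1 comparison already presupposes it.
3. Keep the Section 5.1 comparison of serotyped and unserotyped records, but say that serotyping that differs by vaccination status alone affects the comparators. Add a bounding analysis for joint dependence, which weighting does not remove: vary the VT share among unserotyped vaccinated and unvaccinated patients separately around the observed share, and report the resulting range of VE.

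The cost is protocol wording, a little more analysis and slightly wider comparator intervals. No new data item is needed where sites already hold records on unserotyped patients.

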4.8 Power and sample size and calculation

a) Power calculation

According to the number of cases and controls (i.e. VT-IPD cases and NVT-IPD controls, respectively) collected in the IPD surveillance system, we can calculate the power to detect a given vaccine effectiveness (i.e. 1-odds ratio for vaccination). In order to calculate the power, the following parameters should be taken into account:

- the vaccination coverage in the site;
- number of cases, i.e. VT-IPD;
- number of controls, i.e. NVT-IPD;
- predicted vaccine effectiveness depending on the outcome and exposure;
- a significance level of 5%.

For example, in case of o sample size of 100 VT-IPD cases and 300 NVT-IPD controls, the power will vary according to the vaccination coverage and predicted vaccination effectiveness (Figure 1)

[figure not shown]

Figure 1. Power calculation for different vaccination coverage (VC), vaccine effectiveness, for a sample size of 100 VT-IPD and 300 NVT-IPD

b) Sample size calculation

In case not sufficient number of IPD cases are collected by the surveillance system in a given period of time, the sample size should be calculated in order to reach the desired power and precision of VE estimate. To calculate the sample size, the following parameters should be taken into account:

- a significance level of 5%;
- a power of 80%;
- a precision of 20% around the point VE estimate;
- the vaccination coverage available in the site;
- a vaccine effectiveness of 20%-90% depending on the outcome and exposure;
- a proportion of PPV23-IPD among the all IPD cases of 0.60 (based on SpIDnet1 data in >64 years 2012-2014).

The calculation should be done according to each outcome considered: primary outcome (IPD of vaccine serotypes) and secondary outcomes (specific vaccine serotypes/vaccine related serotypes, clinical manifestation, IPD antimicrobial non-susceptibility and severe IPD of vaccine serotypes).

Table 4 presents the sample size needed to reach the chosen precision around point estimate.

Table 4. Sample size needed for the for different vaccine coverages and vaccine effectiveness.

Precision	Alpha	Power	Proportion of vaccine type/ all cases	Vaccine coverage in the source population	Detectable VE(1-OR)	Number of cases	Number of controls	Total IPD patients included
0.2	0.05	0.8	0.6	0.1	0.9	346	231	576
0.2	0.05	8.0	0.6	0.1	0.8	509	339	849
0.2	0.05	8.0	0.6	0.1	0.7	717	478	1195
0.2	0.05	8.0	0.6	0.1	0.6	963	642	1605
0.2	0.05	8.0	0.6	0.1	0.5	1246	831	2077

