leukemia		Lymphoid and myeloid leukaemia; multiple myeloma		0-no 1-yes 9-unknown	See table 4	
lymphoma		Hodgkin lymphoma, Follicular lymphoma, Non-follicular lymphoma, MatureT/NK-cell lymphoma, Other and unspecified types of non-Hodgkin lymphoma		0-no 1-yes 9-unknown	See table 4	
transplant		Solid organ transplat	Code	0-no 1-yes 9-unknown	See table 4	
malignancy		Generalized malignancy	Code	0-no 1-yes 9-unknown	See table 4	

Variable name	Name of the variable in the site specific database	Variable label	Type	Values and coding	Definition	Comments
immunomed		Immunosuppressing medication	Code	0-no 1-yes 9-unknown	See table 4	
diabetes		Diabetes mellitus	Code	0-no 1-yes 9-unknown	Patient was diagnosed with diabetes mellitus type 1 or 2	
asplenia		Asplenia or splenectomised	Code	0-no 1-yes 9-unknown	Patient with functional or anatomical asplenia / splenectomy in the clinical history	
sicklemia		Sickle cell disease	Code	0-no 1-yes 9-unknown	Patient with sickle cell disease in the clinical history Also include: Thalassemia, Other haemoglobinopathies	
csfleak		Cerebrospinal fluid (CSF) leak	Code	0-no 1-yes 9-unknown	See table 4	
cohlear		Cochlear implant	Code	0-no 1-yes 9-unknown	See table 4	

Variable name	Name of the variable in the site specific database	Variable label	Туре	Values and coding	Definition	Comments
alcoholism		Alcoholism	Code	0-no 1-yes 9-unknown	See table 4	
liverdis		Liver chronic disease including cirrhosis	Code	0-no 1-yes 9-unknown	See table 4	
smoking		Cigarette smoking	Code	0-no 1-yes 9-unknown	See table 4	
institutionalised		Institutionalized persons	Code	0-no 1-yes 9-unknown	See table 4	
otherdis		Other underlying disease	Text	string20	Specify other underlying conditions included in the recommendation for PCV/PPV vaccination.	
Fluvac		Influenza vaccination	Code	0-no 1-yes 9-unknown	Influenza vaccination for the current season	

Variable name	Name of the variable in the site specific database	Variable label	Туре	Values and coding	Definition	Comments
Other variables						Please include all other variables collected in the site specific surveillance system

Table 2: ICD codes for case identification Clinical IPD

ICD-9 Code	ICD-10 Code	Diagnosis in Text
038	A40, A41	Streptococcal sepsis; other sepsis
003.1		
995.91		
041	A49	Bacterial infection of unspecified site
320	G00	Bacterial meningitis, not elsewhere classified
711	M00	Pyogenic arthritis
420	130.1	Infective pericarditis

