041.09	B95.3	S. pneumoniae as the cause of diseases classified to other chapters
041.09	B95.4	Other Streptococcus as the cause of diseases classified to other chapters
041.00	B95.5	Unspecified Streptococcus as the cause of diseases classified to other chapters
995.91 and 790.7		Sepsis with bacteremia ??

SpCAP		
Pneumococcal pneumonia	481	J13

Table 4: ICD codes for the underlying conditions by immune status

Risk conditions	Description	ICD-9 Code	ICD-10 Code
Immunocompromised persons			
Congenital/acquired immunodeficiency		135, 279	D80-D89
Human immunodeficiency virus (HIV) disease		042	B20-B24
Chronic kidney disease		585	N18
Nephrotic syndrome		581	N04
Leukemia	Lymphoid and myeloid leukaemia; multiple myeloma	203 – 205	C91-C92, C90
Lymphoma	Hodgkin lymphoma, Follicular lymphoma, Non-follicular lymphoma, MatureT/NK-cell lymphoma, Other and unspecified types of non- Hodgkin lymphoma	200 – 202	C81, C82, C83, C84, C85
Generalized malignancy			No specific ICD-10 codes
Immunosuppressing medication			No specific ICD-10 codes
Solid Organ Transplant	Transplanted organ and tissue status	V42	Z94
Functional or anatomical asplenia			
Thalassemia, Sickle cell disorders, Other haemoglobinopathies, Diseases of the spleen (including anatomical asplenia)		282, 289.4-5	D56, D57, D58.2, D73
Immunocompetent persons			

Cerebrospinal fluid (CSF) leak		349.81, 388.61	G96.0
Cochlear implant		431	Z96.1
Chronic heart disease	Chronic ischemic heart disease, Cardiomyopathy, Heart failure	412 – 414, 425, 428	125, 142, 150
Chronic lung disease	Emphysema, Other COPD, Asthma	492, 493	J43, J44, J45
Diabetes mellitus	Type 1 Diabetes, Type 2 Diabetes, Malnutrition-related diabetes, Other specified diabetes, Unspecified diabetes	250	E10, E11, E12, E13, E14
Alcoholism	Mental and behavioral disorders due to use of alcohol, Degeneration of nervous system due to alcohol, Alcoholic polyneuropathy, Alcoholic myopathy, Alcoholic cardiomyopathy, Alcoholic liver disease, Alcoholinduced acute pancreatitis, Alcoholinduced chronic pancreatitis, Maternal care for (suspected) damage to fetus from alcohol,	305, 281, 357.5, 425.5, 535.30-31, 571, 655	F10, G31.2*, G62.1, G72.1*, I42.6, K29.2, K70, K85.2*, K86.0*, O35.4
Chronic liver disease, cirrhosis	Hepatic failure, NES, Chronic hepatitis, NES, Fibrosis and cirrhosis, Other diseases of liver, Malignancy of liver	155, 470 – 474	K72, K73, K74, K76, K76.9, C22

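### Appendix 1 cites the wrong code table and the wrong vaccine in its optional validation comparators, which could bias the check on the non-vaccine-serotype controls if followed literally

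*Protocol*

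**What the plan says.** Appendix 1 says that the VE results should be compared with those from other control groups built on the same data sources, to see which group best reflects vaccination coverage in the population producing the vaccine-type cases. It offers these comparators:

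- **Hospital controls, option 1a:** "hospitalised elderly≥65 years for other ICD codes than pneumococcal related codes as presented in Table 4".
- **Hospital controls, option 1b:** admissions for conditions not regarded as high risk for IPD or SpCAP, specified as "ICD9CM 800-999 or ICD10CM: S00-T98: Injury and poisoning".
- **Community controls, screening method:** coverage in a reference group is compared with the vaccinated proportion of cases. Seven example sources of coverage are listed. One reads "a sample of patients in a defined time period may be selected and influenza vaccination status documented"; a second has a catchment-area sample interviewed about the same vaccine. Under Measure of effect, PCV (here the proportion of cases vaccinated, not the conjugate vaccine) is defined as "the proportion of influenza cases vaccinated".

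Three tables bear on option 1a:

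- "Table 4: ICD codes for the underlying conditions by immune status" (Tables, after section 9);
- "Table 2: ICD codes for case identification Clinical IPD" (same place), which also holds the SpCAP code;
- "Table 4. Sample size needed for the for different vaccine coverages and vaccine effectiveness" (section 4.8).

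Section 4.6.2 fixes the exposure as a history of vaccination with PPSV23 or PCV13. Influenza vaccination appears in section 4.7 and Table 3 only as a covariate.

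**The concern.** The indirect cohort design stands or falls on NVT patients having the same vaccination coverage as the source population (section 1.2). Appendix 1 is where a site tests that. A comparator built from the wrong code list, or from coverage with a different vaccine, can disagree with the NVT result, or agree with it, for reasons unrelated to the assumption under test.

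This is a generic protocol that sites are invited to adapt (section 1.2), and a pooled article is planned (section 8). Wording copied into several site protocols would carry the same slip into each.

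**Working it through.** The plan states no figure on this point, so there is none to reproduce. The passages are compared first; the possible consequence is then illustrated.

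**1. Table reference in option 1a.** The ICD Table 4 holds immune disorders, kidney, heart and lung disease, diabetes, liver disease and similar conditions. It holds no code for pneumococcal disease. Those codes are in Table 2, which section 4.5.3 also cites for case identification. Table 3 repeatedly sends the reader to Table 4 for risk conditions, so the protocol's current usage of that number is the risk list. The amendment log explains how the mismatch arose ("Table 4 becomes table 2 and includes ICD codes for clinical IPD and SpCAP"), but the conflict is between passages of the current text.

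**2. Influenza wording.** Two of the seven coverage sources name influenza vaccination; the other five name no influenza vaccine. The definition of PCV names influenza cases, while the sentence introducing the formula names IPD, SpCAP or a serotype outcome.

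**3. Codes in option 1b.** The ICD-9 codes in Table 2 are 003.1, 038, 041 (with 041.00 and 041.09), 320, 420, 481, 711, 790.7 and 995.91. Only 995.91 lies within 800-999. No ICD-10 code in Table 2 lies within S00-T98.

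**4. Illustration.** Appendix 1 gives VE = 1 - odds(vaccinated, cases) / odds(vaccinated, population). If the true pneumococcal coverage is c, the odds in cases are (1 - VE) x c/(1 - c). All coverages below are assumptions, because the documents give none.

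*Influenza coverage used by mistake.* With c = 30% and true VE = 60%, the odds in cases are 0.4 x 0.4286 = 0.1714.
- Influenza coverage 50% (odds 1): 1 - 0.1714 = 82.9%.
- Influenza coverage 70% (odds 2.333): 1 - 0.1714/2.333 = 92.7%.
- With a true VE of 20%, the same two coverages give 65.7% and 85.3%.
- With c = 50% and true VE = 60%, influenza coverage of 50% gives 60% (no bias) and 70% gives 82.9%.
- If influenza coverage is the lower one, the error reverses: c = 30%, true VE = 50% and influenza coverage 20% give 1 - 0.2143/0.25 = 14.3%.

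*Option 1a with Table 4 admissions removed.* True VE = 60%.

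| Source coverage | Control coverage | Apparent VE |
|---|---|---|
| 30% | 25% | 1 - 0.1714/0.3333 = 48.6% |
| 30% | 20% | 1 - 0.1714/0.25 = 31.4% |
| 30% | 15% | 1 - 0.1714/0.1765 = 2.9% |
| 50% | 45% | 1 - 0.4/0.8182 = 51.1% |
| 50% | 35% | 1 - 0.4/0.5385 = 25.7% |

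The fall in control coverage presumes that risk patients are vaccinated more often. Section 1.1 makes this plausible: in the 2013 survey, PPSV23 was targeted at high-risk groups in 15 countries and at those aged 65 or over in six.

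*Vaccine-type cases left among controls.* For option 1a, vaccine-type admissions making up 1% to 5% of controls move a true VE of 60% only to between 59.7% and 58.2%. The 995.91 overlap in 1b is contamination of the same kind.

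**The case against.** The strongest reply is that these are visible leftovers that no careful site would follow. Option 1a speaks of pneumococcal codes, and the ICD Table 4 plainly contains none. Section 4.5.3 points to Table 2. Section 4.6.2 fixes the exposure, and a database of IPD and SpCAP patients has no influenza cases from which to compute PCV. The control groups are ones that could be used, the coverage sources are examples, and each site describes its own validation studies.

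Much of this stands, and it limits the point in four ways:

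- A reader might infer that the validation is bound to give a false answer. The documents do not support that: a site must first choose one of these options and then follow the wording literally.
- A reader might infer that option 1a leaves no risk patients among the controls. It selects on what people are hospitalised for, so on that reading a diabetic admitted with a fracture stays in. The low-coverage rows above are therefore worst cases. They are also crude, whereas sections 4.7 and 5.5 plan to collect and adjust for underlying conditions, and Appendix 1 itself notes the need for adjustment and the risk of selection bias.
- The 995.91 overlap is minor. The text restricts 1b to injury and poisoning, the ICD-10 range is clean, and a case also needs laboratory confirmation and a serotype.
- Replacing the influenza cases by vaccine-type cases only would be wrong, because Appendix 1 applies the screening method to any selected outcome, including all-type IPD or SpCAP.

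The reply does not remove the errors. Option 1b deliberately avoids high-risk conditions, so a site could think 1a does so too. The wider programme covers both influenza and pneumococcal vaccines (section 2) and Table 3 collects influenza vaccination, so the influenza wording does not look out of place. A site that interviewed a sample as written would have collected the wrong exposure.

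**Conclusion.** The point holds in limited form. Option 1a cites the wrong table. Two of the seven coverage sources and the definition of PCV name the wrong vaccine or disease. The ICD-9 range in 1b overlaps Table 2 in one code, which is minor. These are working definitions for a validation that the appendix says should be done, so they should be corrected before sites adapt the text.

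The effect is confined to option 1a, part of the screening method and, marginally, 1b. A reader might infer that the main vaccine effectiveness estimates are compromised; they are not, because the NVT-controlled analysis uses none of these definitions.

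If the wording is followed literally, the distortion of the validation estimate can range from none to several tens of percentage points. It runs downward for 1a if risk patients are vaccinated more often, and upward for the screening method if influenza coverage exceeds pneumococcal coverage. Size and direction rest on assumed coverages, so the figures are illustrations and not estimates.

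**What to change.** Wording changes only, with no new data or analysis:

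- In option 1a, cite Table 2, and give the sample-size table in section 4.8 its own number.
- In the two affected coverage sources, replace influenza vaccination status by PPSV23/PCV13 vaccination status.
- Define PCV as the proportion vaccinated among cases of the selected outcome (IPD, SpCAP or serotype-specific).
- In option 1b, exclude all Table 2 codes from the ICD-9 range, which in practice means 995.91.

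The cost is a short amendment. A site that has already copied Appendix 1 should check which table and which vaccine it used.
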